16.2.1.1.2. AUC_{0-T}

The average effect will be calculated as the AUC divided by the length of the time interval of interest (for example, 12 hours for AUC_{0-12h} or 3 hours for AUC_{0-3h}). AUC will be calculated using the trapezoidal method, as follows:

$$AUC = \frac{1}{2} \sum_{i=1}^{n-1} (T_{i+1} - T_i) (C_{i+1} + C_i)$$

Where T_i is the ith time value, C_i is the ith concentration value, n is the number of time values. The change from the baseline FEV₁ to average FEV₁ (AUC) will be summarised and analysed.

Document: ...\\Verona_Pharma\\RPL554\\BZA48916\\Biostatistics\\Documentation\\SAP\\Verona CO-205 SAP v1.0

Author: [REDACTED] Version Number: V1.0

Version Date: 05DEC2019

Template No.: CS_TP_BS016 Revision 5

Reference: CS_WI_BS005

Effective Date: 01Apr2018

If two last data points are missing the AUC is set to missing, that is for AUC_{0-12h} we require at least up to 8 hours of assessments and for AUC_{0-3h} we require at least up to 2 hours of assessments. If first measurement for the calculation of the AUC is missing, then the AUC will not be calculated.

16.2.1.2. *DIARY DATA*

16.2.1.2.1. *E-RSTM: COPD*

Evaluating Respiratory Symptoms for COPD (E-RSTM: COPD) data will be collected within EXACT-PRO questionnaire (consisting of 14 questions), as shown in the Appendix 4. Please note that items 3, 8, 9, 10, 11 and 14 have separate scoring instructions, namely with the same raw score being assigned to several answer options. E-RSTM: COPD consists of 11 questions, with subdomains of: Breathlessness, Cough and Sputum, and Chest Symptoms. This data will be collected everyday throughout the duration of the study.

Calculating the score

E-RS subdomains:

- Breathlessness – items 7, 8, 9, 10 and 11 (score range: 0-17)
- Cough and Sputum – items 2, 3 and 4 (score range: 0-11)
- Chest Symptoms – items 1, 5 and 6 (score range: 0-12)

Total and subdomain scores are derived weekly as the mean over total number of days between previous visit (inclusive) and the following visit, using only days where data was recorded. For the last visit, when patient completes the study the derivation will use days between previous visit (inclusive) and the following/last visit (inclusive). Baseline is the mean over the 7 days prior to the first intake of study treatment, using only days where data was recorded. If less than 4 days of data are available for the week, the weekly mean is set to missing, e.g. if data is entered for less than 4 days between Visits 2 and 3 then no result will be presented for Week 1. Furthermore, all questions need to be answered to be evaluable for that day.

If a patient discontinued then use treatment study end date, as the date of their last expected visit.

The EXACT-PRO total score will be calculated by first summing all raw scores and then looking up the corresponding EXACT-PRO total score in the table described in the Appendix 5.

E-RS subdomain score is calculated as the sum from the relevant questions.

16.2.1.2.2. *SGRQ-C*

St. George's Respiratory Questionnaire – COPD specific (SGRQ-C) is a questionnaire consisting of 14 questions, split into two parts. Part 1 consists of the first 7 questions and is related to the Symptoms subdomain. The remaining 7 questions are in Part 2, which are related to the Activity and Impacts subdomains. Each possible answer to each question has a weight assigned described in the Appendix 6.

Document: ...\\Verona_Pharma\\RPL554\\BZA48916\\Biostatistics\\Documentation\\SAP\\Verona CO-205 SAP v1.0

Author:  Version Number: V1.0

Version Date: 05DEC2019

Template No.: CS_TP_BS016 Revision 5

Reference: CS_WI_BS005

Effective Date: 01Apr2018

Calculating the score

Subdomains:

- Symptoms – items 1 to 7
- Activity – items 9 and 12
- Impacts – items 8, 10, 11, 13 and 14

The score for each component is calculated separately by dividing the summed weights by the maximum possible weight for that component and expressing the result as a percentage. A positive component has a non-zero response. It is not possible to have missing items in the questionnaire, as the data is collected in the e-diary which doesn't allow patients to skip between items.

$$Score = 100 * \frac{\text{Sum of weights from all positive items in that component}}{\text{Sum of maximum weights for all items in that component}}$$

The total score is calculated similarly

$$Score = 100 * \frac{\text{Sum of weights from all positive items in that questionnaire}}{\text{Sum of maximum weights for all items in that questionnaire}}$$

The higher the score the more severe impact of COPD on patient's life.

16.2.1.2.3.□□□□□ BDI/TDI

BDI and TDI are questionnaires that focus on three subdomains: Functional impairment, Magnitude of task and Magnitude of effort. BDI is collected at baseline (Day 1) and TDI is collected post-baseline (Weeks 2 and 4).

Subdomain score is calculated as the sum from the related questions.

Total score is calculated as the sum of the subdomain scores.

If at least one of the scores is missing, then total score is set to missing.

16.2.1.2.4.□□□□□ PGAC

Patient Global Assessment of Change (PGAC) is a single question assessment to determine whether patients have noticed a change in their breathing since the start of the study.

16.2.1.2.5.□□□□□ CAT

CAT is designed to assess further the COPD symptoms. There are 8 subdomains, each having only one question and these include Cough, Mucus, Chest Tight, Breathless, Limited Activities, Confident, Sleep and Energy. Each question is scored 1-5. The higher the score the more severe impact of COPD on patient's life.

Document: ...\\Verona_Pharma\\RPL554\\BZA48916\\Biostatistics\\Documentation\\SAP\\Verona CO-205 SAP v1.0

Author: [REDACTED] Version Number: V1.0

Version Date: 05DEC2019

Template No.: CS_TP_BS016 Revision 5

Reference: CS_WI_BS005

Effective Date: 01Apr2018

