16.4. Missing Data Methods for Efficacy Variables

Data for calculation of average (AUC) effects for FEV₁ will be imputed if the pre-dose is not missing. This will be done using the following method:

- ‘bounded’ missing data will use interpolation through the trapezoidal method described in section 16.2.1.1.2,
- ‘unbounded’ missing data will not be imputed
 - If last measurement is missing, then the AUC will be calculated up to the point where data is not missing, however if two or more last measurements will be missing, then the AUC will be set to missing.
 - If first measurement is missing, the AUC will not be calculated and set to missing.

For the analysis of responder on SGRQ-C and CAT missing responses will be treated as indicating non-responders in the analysis.

All other missing data, including for when pre-dose is missing, will not be imputed.

For the sensitivity and interim analysis missing data will be imputed using LOCF method. In cases where patient discontinues early and has spirometry data reported at the EOS visit, the following strategy explained below will be used.

1. Check the visit day at which EOS visit was performed against the following window for

Document: ...\\Verona_Pharma\\RPL554\\BZA48916\\Biostatistics\\Documentation\\SAP\\Verona CO-205 SAP v1.0

Author: [REDACTED] Version Number: V1.0

Version Date: 05DEC2019

Template No.: CS_TP_BS016 Revision 5

Reference: CS_WI_BS005

Effective Date: 01Apr2018

each visit:

- a. Day 1 = Day 1
- b. Week 1 = after day 1 and up to and including day 9
- c. Week 2 = after day 9 and up to and including day 16
- d. Week 3 = after day 16 and up to and including day 23
- e. Week 4 = after day 23 and up to and including day 30

2. Set the value for the corresponding visit, and any subsequent visits, to be the value from EOS. If the corresponding visit has a measurement already, then the next available visit must be used for EOS.
3. If there are missing values before the EOS corresponding visit, we would impute using LOCF in the usual manner.

In the case where patient discontinues early and did not have spirometry data recorded at the EOS visit, or cases of missing data for patients who did not discontinue early, LOCF will be applied in the usual manner.

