16.5. Sensitivity analysis for Efficacy Variables

Sensitivity analyses will be done for the primary endpoint (change from baseline FEV₁ to peak FEV₁ at Week 4) and for key secondary endpoints (change from baseline FEV₁ to average AUC_{0-12h} FEV₁ at Week 4, and change from baseline in total E-RSTM:COPD score at Week 4). An ANCOVA approach will be used to compare treatment groups, with fixed factors for treatment and actual reversibility strata, and the baseline result as a covariate. RPL554 treatments will be compared to placebo and to each other, as described in Section 16.1.2.

As a sensitivity analysis, the primary analysis (i.e. MMRM) of the efficacy endpoints described above will be repeated on the PPS set.

Furthermore, an analysis of the proportion of patients with an improvement from baseline in SGRQ-C total score of 4 or more will be summarised by visit and treatment group and analysed using logistic regression. The model will include randomised treatment groups and actual reversibility strata as factors. Patients with a missing response will be handled according to last known responder status (LOCF).

Any missing data post-baseline will be imputed using the LOCF method described in Section 16.4.

Sensitivity analysis, with respect to impact of rescue use during clinic visits, will only be performed if at least one patient is excluded from this analysis due to taking rescue medication within 6 hours of spirometry test. Patient can only be excluded from the analysis if enough of the spirometry tests are affected for the function tests not being able to be calculated, i.e. if first

Document: ...\\Verona_Pharma\\RPL554\\BZA48916\\Biostatistics\\Documentation\\SAP\\Verona CO-205 SAP v1.0

Author: [REDACTED] Version Number: V1.0

Version Date: 05DEC2019

Template No.: CS_TP_BS016 Revision 5

Reference: CS_WI_BS005

Effective Date: 01Apr2018

FEV₁ measurement is affected by the rescue medication then AUC cannot be calculated for that visit.

This additional sensitivity analysis, taking into account rescue medication, will be performed for a secondary endpoint, change from baseline FEV₁ to average AUC_{0-12h} FEV₁ at Week 4.

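### The SAP gives no divisor for an FEV1 or FVC AUC that stops early because the last reading is missing; the only divisors it names would make that patient's average about one third too low

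*SAP*

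**What the plan says.** SAP 16.2.1.1.2 computes the AUC of absolute FEV1 by the trapezoidal rule, converts it to an average, and only then takes the change from baseline. On the conversion it says: "The average effect will be calculated as the AUC divided by the length of the time interval of interest (for example, 12 hours for" AUC0-12h, and 3 hours for AUC0-3h. Protocol 9.4.5 has the same rule without any hours, and Protocol 9.4.8 leaves AUC imputation to the SAP.

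On incomplete profiles, SAP 16.4 says of gaps with readings on both sides that "missing data will use interpolation through the trapezoidal method described in section 16.2.1.1.2". Of gaps at an end it says that "missing data will not be imputed". It then adds: "If last measurement is missing, then the AUC will be calculated up to the point where data is not missing". Two or more missing readings at the end make the AUC missing. SAP 16.2.1.1.2 agrees: for AUC0-12h, "we require at least up to 8 hours of assessments", and for AUC0-3h, up to 2 hours.

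SAP 16.4 names only FEV1 here, but SAP 7.2 refers to it for both FEV1 and FVC. SAP 16.5 counts the Week 4 AUC0-12h among the "key secondary endpoints (change from baseline" FEV1, followed by the average AUC).

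**The concern.** A profile cut at 8 h contributes 8 hours of area. Divided by 12, it is no longer an average of anything the patient blew: it treats the last four hours as if FEV1 had been zero. The same happens with 2 hours of area divided by 3. Because baseline is subtracted after averaging, the whole shortfall lands on the change from baseline, which is the analysed quantity.

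The exposed results are AUC0-12h at Day 1 and Week 4 and AUC0-3h at Weeks 1 to 3, where 3 h is the last scheduled reading. At Day 1 and Week 4 a missing 3 h reading has the 4 h reading beyond it, but the SAP does not say whether that reading may be used for AUC0-3h.

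The planned sensitivity analyses would not repair the error. A truncated AUC is a recorded value and not a missing one, so the ANCOVA with last observation carried forward and the per-protocol repeat would both reuse it.

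**Working it through.** **Plan's own figures.** The documents give no figure for a truncated AUC. The only related design figure is the sample size for peak FEV1 in Protocol 9.5, which reproduces: 2 × (1.96 + 0.84)² × 200² / 93² = 72.5, so 73 per group. Its SD of 200 mL serves below only as a scale.

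**Inputs from the documents.** Protocol Table 4 schedules post-dose readings at 0.5, 1, 2, 3, 4, 6, 8 and 12 h (Visits 2 and 6), and at 0.5, 1, 2 and 3 h (Visits 3 to 5). The retained profiles end at 8 h or 2 h.

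**Assumptions.** The pre-dose reading is placed at time 0, since the SAP gives it no time value. FEV1 is taken as 1.0, 1.3 or 1.5 L, since the documents give no mean FEV1.

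**Formula.** Value with the named divisor minus full-data value:
- AUC0-12h: −(1/12) × area from 8 to 12 h = −(1/3) × mean FEV1 over 8–12 h
- AUC0-3h: −(1/3) × area from 2 to 3 h = −(1/3) × mean FEV1 over 2–3 h

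**Flat profile.** −1000/3, −1300/3 and −1500/3 give −333, −433 and −500 mL for both endpoints. That is 1.7 to 2.5 times the 200 mL SD (333/200, 500/200). With the observed divisor the error is zero.

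**Assumed response curve.** Let FEV1 be the base value plus 0, 220, 250, 250, 240, 220, 180, 150 and 100 mL at 0, 0.5, 1, 2, 3, 4, 6, 8 and 12 h. The areas of the response are 422.5 (0–2 h), 667.5 (0–3 h), 1627.5 (0–8 h) and 2127.5 mL·h (0–12 h).

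Full data: 2127.5/12 = +177.3 mL and 667.5/3 = +222.5 mL. With the last reading missing and the named divisor, at a base of 1.0 L: (8 × 1000 + 1627.5)/12 − 1000 = −197.7 mL, and (2 × 1000 + 422.5)/3 − 1000 = −192.5 mL.

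| Endpoint | Base (L) | True change (mL) | Named divisor (mL) | Error (mL) |
|---|---|---|---|---|
| AUC0-12h | 1.0 | +177.3 | −197.7 | −375.0 |
| AUC0-12h | 1.3 | +177.3 | −297.7 | −475.0 |
| AUC0-12h | 1.5 | +177.3 | −364.4 | −541.7 |
| AUC0-3h | 1.0 | +222.5 | −192.5 | −415.0 |
| AUC0-3h | 1.3 | +222.5 | −292.5 | −515.0 |
| AUC0-3h | 1.5 | +222.5 | −359.2 | −581.7 |

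**Observed divisor, same curve.** 1627.5/8 = +203.4 mL (residual +26.1) and 422.5/2 = +211.3 mL (residual −11.3). If the assumed 12 h response runs from 150 down to 0 mL, the 0–12 h residual is +17.8 to +42.8 mL. If the assumed 3 h response runs from 200 to 270 mL, the 0–3 h residual is −4.6 to −16.2 mL.

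**Missing 3 h reading at Day 1 or Week 4.** Interpolating between 2 h and 4 h gives (250 + 220)/2 = 235 mL at 3 h, and an average of (422.5 + 242.5)/3 = +221.7 mL against a true +222.5 mL.

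**Time of the pre-dose point.** If it were entered at −0.5 h, the truncated flat profile would be 8.5/12.5 or 2.5/3.5 of the full-data value, that is 32.0% or 28.6% too low. The shortfall in mL is unchanged.

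**Scaling to an arm difference.** Each percentage point by which the affected share differs between two arms moves their difference by 0.01 × the error: 3.3 to 5.0 mL on the flat profile, and on the curve about 3.8 to 5.4 mL (0–12 h) or 4.2 to 5.8 mL (0–3 h). One percent of an 80-patient arm is 0.8 of a patient.

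**The case against.** The strongest reply is that the SAP never tells anyone to divide 8 hours of area by 12. The hours are given as examples, and the interval of interest for a truncated profile can sensibly be read as the interval integrated. On a roughly flat profile the other reading gives an average below every value the patient produced. This stands as a reason not to call the text an instruction to err. It does not close the gap: 12 h is attached by name to AUC0-12h, and two programmers following the text could differ by more than 300 mL for one patient.

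Such a value might also be noticed, since SAP 6.5 calls for minima and maxima. That is a chance of detection and not a rule.

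Frequency is a fair objection too. Protocol 7.2.1 allows up to eight efforts per time point, and SAP 16.2.1.1.1 uses borderline readings, so losing a reading on quality alone should be uncommon.

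A reader might infer that rescue use feeds the error into the main analysis. The documents do not support that. Exclusion "due to taking rescue medication within 6 hours of spirometry test" appears only in the rescue-use sensitivity analysis of Week 4 AUC0-12h in SAP 16.5. That analysis runs only if at least one patient is excluded, and "Patient can only be excluded from the analysis if enough of the spirometry tests are affected" for the parameter to be incalculable. Once it runs, a patient who loses only the 12 h reading would stay in with an 8 h profile, so the divisor matters there. Protocol 5.9.1 asks patients to withhold short-acting bronchodilators until spirometry is complete, although Protocol 5.10 provides for recording use at visits. Whether such use differs by arm is not known.

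A reader might also infer that every AUC0-3h at Day 1 and Week 4 is truncated, because the SAP 16.2.1.1.1 list omits 3 h at those visits. But Protocol Table 4 schedules that reading and SAP 3.2 defers to the protocol schedule, so this is better read as a list to correct.

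**Conclusion.** The concern holds as a gap in the derivation rule that should be closed. For a patient missing only the last reading, the divisors the SAP names would understate average FEV1 by one third of the mean FEV1 over the unobserved tail. The millilitre figures rest on assumed FEV1 levels and an assumed response curve, and apply only if the named divisors are used. Under the observed span, which the wording also allows, only the small residual remains.

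The gap reaches the secondary AUC endpoints for FEV1, and for FVC through SAP 7.2. It does not reach the primary peak FEV1. The label of key secondary endpoint serves in SAP 16.5 to select endpoints for sensitivity analysis; SAP 7.3 orders doses and gives AUC0-12h no ranked place. A bias in the treatment comparisons cannot be inferred: the documents give neither the rate of missing last readings nor its balance across arms, and they plan no power for the AUC endpoints.

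**What to change.** In SAP 16.2.1.1.2 and 16.4, for both FEV1 and FVC:
- State that when the last reading is missing, the truncated AUC is divided by the time actually integrated, that is the last observed time minus the time assigned to the pre-dose point.
- State that time value. With 0 h, the divisors are 8 h and 2 h.
- State that a missing 3 h reading at Day 1 or Week 4 is interpolated between 2 h and 4 h for AUC0-3h.

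Apply the same divisor in the rescue-use analysis of SAP 16.5. Separately, restore the 3 h reading to the Day 1 and Week 4 list in SAP 16.2.1.1.1 to match Protocol Table 4.

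This keeps the SAP's rule of retaining 8 h and 2 h profiles. Its price is the residual bias per affected patient shown above, about +18 to +43 mL for 0–12 h and −5 to −16 mL for 0–3 h on the assumed curves. Setting such AUCs to missing would avoid that residual but reverse the retention rule and discard the observed hours. The cost is a few sentences, one line of derivation code and one corrected list; no further data are needed.

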16.2.1.3. COPD EXACERBATIONS

Patients with at least one AE meeting both the following criteria will be included in the analysis of exacerbations:

- MedDRA LLT = "COPD exacerbation"
- Use of a systemic steroid (ATC2=H02) at or after the AE date of onset and before the end date, lasting for at least 3 days

16.2.1.4. RESCUE MEDICATIONS

Rescue medication use will be presented for the FAS set.

Baseline use of rescue medication is the mean over the last 7 days of run-in phase, using only days where data was recorded:

$$\frac{\text{Sum of number of puffs taken}}{\text{days recorded}}$$

Use of medication per visit is calculated as the mean use daily over total number of days between previous visit (inclusive) and the following visit, e.g. Week 1 is defined as the period between Visit 2 and Visit 3, calculated only based on the days data was recorded/verified. For the last visit, when patient completes the study the derivation will use days between previous visit (inclusive) and the following/last visit (inclusive).

If less than 4 days of data are available for the week, the weekly mean is set to missing, e.g. if data is entered for less than 4 days between Visits 2 and 3 then no result will be presented for Week 1.

If a patient discontinued then use treatment study end date, as the date of their last expected visit. This will be documented in the "Rescue Medication" page of the eCRF, as well as in the "Rescue Medication Use" diary entry.

The rescue medication use will be confirmed in the diary using the following rules:

1. If patient has put in rescue medication use then analyse as expected
2. If patient has not put in rescue medication use, then to confirm that there was no diary compliance issue, or IT issue, question "No Rescue Medication Confirmation" will be checked to make sure it is filled in correctly.
3. If patient has not put in rescue medication use and question "No Rescue Medication Confirmation" was not filled in correctly then this will be treated as diary compliance or IT issue and therefore this day will not be used as the day recorded for the weekly means calculation.

